6.3. Study Duration and Period

The expected total duration of study participation for each randomized patient is approximately 57 weeks. The study will consist of an approximately 1-week screening period, a 4-week placebo run-in period, and a 52-week of treatment period.

6.4. End of Study

The study will end when the last randomized patient completes the Week 52 visit. The estimated overall duration of the study (first patient first visit [FPFV] to last patient last visit [LPLV]) is approximately 21 months.

6.5. Number of Patients

The study will enroll approximately 750 adult male and female HeFH and/or ASCVD patients with hyperlipidemia from approximately 125 clinical sites.

6.6. Patient Identification Numbers

A unique patient identification number will be assigned to each patient to identify each patient throughout the study and will be entered on all documentation. If a patient is not eligible to receive treatment, or if a patient discontinues from the study, their patient identification number cannot be assigned to another patient.

Patient identification numbers will be assigned sequentially by interactive web response system (IWRS) at the time of informed consent during the screening module transaction. Screening and Placebo Run-in Period

Screening will occur approximately 5 weeks prior to Day 1 (Visit T1) where the patient's eligibility will be evaluated. Eligible patients who are taking allowed concomitant medications must be on stable regimens as defined in [Section 8.2](#). At the investigator's discretion, screening (time between visits S1 and S2) may be extended for an additional 4 weeks if needed to adjust background medical therapy or for other reasons as specified in the protocol. Eligible patients will return to the clinical site at Week -4 (Visit S2) to initiate administration of single-blind (patient only) placebo. Eligible patients will return at Week -1 (Visit S3) for lipid and safety laboratories and an assessment of tolerability and study drug adherence (see [Section 7.1](#) and [Section 7.2](#) for eligibility criteria). Patients who are deemed not eligible for randomization at any point during screening will be notified by clinical site personnel regarding their eligibility status and considered screen failures. As necessary, for reasons of safety if a patient begins the run-in period but screen fails prior to randomization, the patient may be asked to return to the clinical site for further evaluation and follow-up of AEs.

6.6.1. Randomization and Treatment Period

For patients who satisfy all entry criteria and complete the 1-week screening period and 4-week run-in period, randomization will occur and their randomization number will be assigned via IWRS at Week 0 (Visit T1). Patients will be stratified on CV risk (HeFH and ASCVD diagnosis) and baseline statin intensity (high intensity statin, moderate intensity statin, low intensity statin), and randomized in a ratio of 2:1 to receive 1 of the 2 following treatments in a double-blind fashion:

- Bempedoic acid 180-mg tablet
- Matching placebo tablet

For details regarding the randomization strata see [Table 3](#).

7. SELECTION AND WITHDRAWAL OF PATIENTS

7.1. Subject Inclusion Criteria

Each patient with hyperlipidemia must meet the following criteria to be randomized in this study:

1. Provision of written informed consent prior to any study-specific procedure
2. Age ≥ 18 years or legal age of majority based on regional law, whichever is greater at Week -5 (Visit S1)
3. Men and nonpregnant, nonlactating women.
4. Women must be either:
 - Naturally postmenopausal (as reported by the patient, defined as greater than 55 years and ≥ 1 year without menses, <55 years and ≥ 1 year without menses with follicle-stimulating hormone (FSH) ≥ 40.0 IU/L), or surgically sterile including hysterectomy, bilateral oophorectomy, or tubal ligation or;
 - Women of childbearing potential must be willing to use 2 acceptable methods of birth control (unless they have agreed to follow the definition of true abstinence). The minimal requirement for adequate contraception it is that it should be started on Day 1, continuing during the study period, and for at least 30 days after the last dose of study drug. Acceptable methods of birth control include: oral, implantable, injectable or topical birth control medications; placement of an intrauterine device (IUD) with or without hormones; barrier methods including condom or occlusive cap with spermicidal foam or spermicidal jelly; vasectomized male partner who is the sole partner for this patient; or true abstinence when this is in line with the preferred and usual lifestyle of the subject (periodic abstinence [eg, calendar, ovulation, symptothermal, postovulation methods], declaration of abstinence for the duration of the trial, and withdrawal are not acceptable methods of contraception).

There are no protocol-specific birth control requirements for men with partners who are able to become pregnant.

5. Fasting LDL-C (minimum of 10 hours) value at Week -5 (Visit S1) ≥ 100 mg/dL (2.6 mmol/L) and fasting LDL-C value at Week -1 (Visit S3) ≥ 70 mg/dL (1.8 mmol/L).
6. Have high CV risk that is defined as either:
 - Diagnosis of HeFH. Diagnosis must be made by either genotyping or by clinical assessment using either the World Health Organization (WHO) criteria/Dutch Lipid Clinical Network Criteria with a score that is >8 points (see [Appendix 4](#)) or the Simon Broome Register Diagnostic Criteria with an assessment of 'Definite HeFH' (see [Appendix 5](#)). Patients with a diagnosis of HeFH may or may not have established CHD or CHD risk equivalents.

OR

- Have ASCVD (with established CHD or CHD risk equivalents)
Documented history of CHD (includes 1 or more of the following):
 - Acute MI
 - Silent MI
 - Unstable angina
 - Coronary revascularization procedure (eg, percutaneous coronary intervention [PCI] or coronary artery bypass graft [CABG] surgery)
 - Clinically significant CHD diagnosed by invasive or non-invasive testing (such as coronary angiography, stress test using treadmill, stress echocardiography or nuclear imaging)

Documented CHD risk equivalents (includes 1 or more of the following criteria):

- Symptomatic peripheral arterial disease (PAD) defined as
 - Peripheral vascular disease with symptoms of claudication or resting limb ischemia with either ankle brachial index <0.9 performed by a vascular lab or
 - Angiogram (including computed tomographic angiography [CTA]) showing $\geq 50\%$ stenosis or
 - Peripheral arterial revascularization (surgical or percutaneous) occurring greater than 90 days prior to Visit S1 or
 - Lower extremity amputation due to peripheral vascular disease occurring greater than 90 days prior to Visit S1
- Cerebrovascular atherosclerotic disease defined by:
 - ischemic stroke occurring greater than 90 days prior to Visit S1 or
 - Carotid endarterectomy, carotid stenting, or more than 70% stenosis in a carotid artery determined by carotid ultrasound or angiogram occurring greater than 90 days prior to Visit S1.

Note: Patients with T2DM are allowed in this study; however, for this study T2DM is not considered a CHD risk equivalent

7. Be on maximally tolerated lipid-modifying therapy, including a maximally tolerated statin either alone or in combination with other lipid-lowering therapies, at stable doses and regimens for at least 4 weeks prior to screening (6 weeks for fibrates; however, gemfibrozil is not allowed as per co-administration instructions defined in the statin label). Maximally tolerated statin includes statin regimens other than daily dosing, including no to very low doses, but reasons for not using high-intensity statin dosing must be documented.

A patient's maximally tolerated lipid-modifying therapy will be determined by the investigator using their medical judgment and available sources, including the patient's self-reported history of lipid-modifying therapy.

Note: Patients can be on any available lipid-modifying therapy with the exception of the exclusions listed below as long as they have been stable for 4 weeks prior to Screening Visit S1 and are taken at a consistent time each day. In the case of PCSK9 inhibitor use, the patient must have received 3 stable doses. It is important that lipid values are measured at PCSK9i trough levels. Therefore, study visits should be scheduled in accordance with the patient's PCSK9i injection regimen so that measurement of lipid values for all visits occurs before the PCSK9i injection but not greater than 48 hours before the next scheduled PCSK9 injection. Patients who have discontinued investigational or commercial PCSK9 inhibitor must have had their last dose at least 4 months prior to Screening Visit S1.

7.2. Subject Exclusion Criteria

Patients who meet any of the following criteria will not be randomized:

1. Total fasting (minimum of 10 hours) triglyceride ≥ 500 mg/dL (5.6 mmol/L) at Week -5 (Visit S1)

Note: TG may be repeated 1 time between Visits S1 and S2. For those patients who have a repeat TG, the repeat value will be used to determine eligibility.

2. Renal dysfunction or nephritic syndrome or a history of nephritis, including estimated glomerular filtration rate (eGFR) (using central laboratory determined Modification of Diet in Renal Disease [MDRD] formula) < 30 mL/min/1.73m² at Week -5 (Visit S1) (Levey 2006).

Note: At the discretion of the investigator, the screening period may be extended up to 4 weeks for a single repeat eGFR. For those patients who have a repeat eGFR, the repeat value should be obtained between visits S1 and S2 and will be used to determine eligibility.

3. Body mass index (BMI) ≥ 50 kg/m²
4. Recent (within 3 months prior to the screening visit [Week -5 (Visit S1)] or between screening and randomization visits) MI, unstable angina leading to hospitalization, uncontrolled, symptomatic cardiac arrhythmia (or medication for an arrhythmia that was started or dose changed within 3 months of screening), CABG, PCI, carotid surgery or stenting, cerebrovascular accident, transient ischemic attack (TIA), endovascular procedure or surgical intervention for peripheral vascular disease or plans to undergo a major surgical or interventional procedure (eg, PCI, CABG, carotid or peripheral revascularization). Patients with implantable pacemakers or automatic implantable cardioverter defibrillators may be considered if deemed by the Investigator to be stable for the previous 3 months.
5. Uncontrolled hypertension, defined as sitting systolic blood pressure (SBP) ≥ 160 mmHg and diastolic blood pressure (DBP) ≥ 100 mmHg after sitting quietly for 5 minutes

Note: If the initial blood pressure (BP) values meet or exceed the specified level, an additional BP assessment may be completed. If the systolic or the diastolic values continue to meet or exceed the threshold, the patient may not continue screening. However, at the discretion of the Investigator, the screening period (between Visits S1

and S2) may be extended up to 4 weeks to allow for a repeat qualifying BP assessment following adjustment of BP medication(s), provided that the patient has been on a stable dose of the BP medication for a minimum of 2 weeks prior to randomization and the repeat BP measurements do not meet the exclusion criteria.

6. Hemoglobin A_{1C} (HbA_{1C}) $\geq 10\%$ at Week -5 (Visit S1)
7. Uncontrolled hypothyroidism, including thyroid-stimulating hormone (TSH) $> 1.5 \times$ the upper limit of normal (ULN) at Week -5 (Visit S1). Patients stabilized on thyroid replacement therapy for at least 6 weeks prior to randomization are allowed.
8. Liver disease or dysfunction, including:
 - Positive serology for hepatitis B surface antigen (HBsAg) and/or hepatitis C antibodies (HCV-AB) at Week -5 (Visit S1); or
 - Alanine aminotransferase (ALT), aspartate aminotransferase (AST) $\geq 2 \times$ ULN, and/or total bilirubin (TB) $\geq 1.2 \times$ ULN at Week -5 (Visit S1). If TB $\geq 1.2 \times$ ULN, a reflex indirect (unconjugated) bilirubin will be obtained and if consistent with Gilbert's disease or if the patient has a history of Gilbert's Disease, the patient may be enrolled in the study.

Note: At the discretion of the investigator, a single repeat of ALT and/or AST may be completed prior to randomization. For those patients who have a repeat ALT and/or AST, the repeat value will be used to determine eligibility. Also, if test for hepatitis C antibody is positive, but reflexive test for Hepatitis C ribonucleic acid (RNA) is negative, patient can be enrolled.

9. Gastrointestinal conditions or procedures (including weight loss surgery; eg, Lap-Band[®] or gastric bypass) that may affect drug absorption
10. Hematologic or coagulation disorders or a hemoglobin (Hgb) level < 10.0 g/dL (100 g/L) at Week -5 (Visit S1)
11. Active malignancy, including those requiring surgery, chemotherapy, and/or radiation in the past 5 years. Nonmetastatic basal or squamous cell carcinoma of the skin and cervical carcinoma in situ are allowed.
12. Unexplained creatine kinase (CK) $> 3 \times$ ULN at screening up to randomization (ie, not associated with recent trauma or physically strenuous activity). Patients with an explained CK elevation must have single repeat CK $\leq 3 \times$ ULN prior to randomization.
13. History within the last 2 years of drug, alcohol, amphetamine and derivatives, or cocaine abuse. Patients with amphetamine derivatives prescribed by and under the care of a health care practitioner can be enrolled after evaluation by the Investigator.
14. Blood donation, blood transfusion for any reason, participation in a clinical study with multiple blood draws, major trauma, or surgery with or without blood loss within 30 days prior to randomization
15. Use of any experimental or investigational drugs within 30 days prior to screening.
16. Previous enrollment in a bempedoic acid clinical study.

17. Use of any of the following drugs or a plan to use these drugs during the study;
 - New or planned dose changes of systemic corticosteroids. Stable doses (≥ 4 weeks before Visit S1) and topical steroids allowed.
 - CETP inhibitors within the last 2 years prior to screening (Week -5, Visit S1) except for evaceptrapib within the last 3 months prior to screening (Week -5, Visit S1)
 - Mipomersen (6 months prior to screening, Week -5, Visit S1)
 - Lomitapide (3 months prior to screening, Week -5, Visit S1)
 - Apheresis (3 months prior to screening, Week -5, Visit S1)
 - Simvastatin ≥ 40 mg/day (4 weeks prior to screening, Week -5, Visit S1)
 - Red yeast rice extract-containing products are not allowed (2 weeks prior to screening, Week -5, Visit S1)
18. Planned initiation of the following drugs during the clinical trial or changes prior to randomization (Day 1, Visit T1):
 - Hormone replacement (6 weeks prior to randomization)
 - Thyroid replacement (6 weeks prior to randomization)
 - Diabetes medications (4 weeks prior to randomization)
 - Obesity medication (44 weeks prior to randomization)
19. Lack of adherence (ie, less than 80% of planned doses) with IMP (single-blind placebo) during the Run-in Period.
20. Lack of tolerance with IMP (single-blind placebo) during the Run-in Period.
21. A medical or situational (ie, geographical) finding that in the investigator's opinion may compromise the patient's safety or ability to complete the study.
22. An employee or contractor of the facility conducting the study, or a family member of the Principal Investigator, Co-Investigator, or Sponsor.
23. Pregnant, breastfeeding, or intending to become pregnant within 30 days after last dose of study drug.
24. Patients who have enrolled in a study of an experimental siRNA inhibitor of PCSK9 are excluded.

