10.2.1. Screening Week -5 (Visit S1; Day -35 ± 7 days)

The screening period will begin with a screening visit that will occur approximately 5 weeks prior to randomization. Visit S1 will allow the Investigator to assess the patient's preliminary eligibility. After the patient provides written informed consent (see [Section 10.1](#)), the patient will undergo the following assessments and procedures at Visit S1:

- Demographics
- Clinically relevant medical history, including assessment of HeFH status and ASCVD
- Concomitant and prohibited medication review
- Height (cm), weight (kg), BMI
- Vital signs
- Clinical laboratory evaluations:
 - Hematology, blood chemistry, coagulation, and urinalysis
 - Basic fasting lipids (TC, calculated LDL-C, HDL-C, non-HDL-C, and TG)
 - HbA_{1C}
 - TSH
 - FSH (in appropriate female patients)
 - Serum pregnancy test (on appropriate female patients)
- Serology (including HBsAg, HCV)

- Review of all inclusion/exclusion criteria that can be assessed at this time
- Conduct diet and exercise counseling
- Contact IWRS to register the patient

Patients who meet all enrollment criteria that can be assessed at Visit S1 will be instructed to continue their therapy(s) for lipid regulation and to maintain consistent diet and exercise patterns throughout the study. Patients who fail to meet any entry criterion that can be assessed at Visit S1 are considered to be screen failures and are not required to return for additional visits (although a patient can be seen at any time for safety reasons).

Note:

- An optional visit approximately 1 week later MAY be completed if patient fails TG entry criterion. If this optional visit is completed, the repeat lipid values will be used to determine eligibility.
- An optional visit between Visits S1 and S2 may be scheduled to collect screening fasting labs in the event that the patient arrives at Visit S1 in a nonfasted state.
- An optional visit between Visits S1 and S2 may be completed if the patient's DBP and/or SBP meet the exclusion criteria levels. Patients may randomize after BP medications have been adjusted, they have been on stable doses of BP medications for at least 2 weeks, and the repeat BP values (DBP and/or SBP) no longer meet exclusionary values.

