- ² An optional visit between Visits S1 and S2 may be completed if the patient's DBP and/or SBP meet the exclusion criteria levels. Patients may randomize after blood pressure medications have been adjusted, the patients have been on stable doses of blood pressure medications for at least 2 weeks, and the repeat blood pressure values (DBP and/or SBP) do not meet exclusionary values. An optional visit between Visit S1 and S2 may be completed to determine eligibility if the patient's eGFR, ALT, AST, and/or TB meet exclusion criteria levels. If this optional visit is completed, the repeated value will be used to determine eligibility.
- ³ All procedures will be completed for all patients at either End of Study (EOS) if completing the study or early withdrawal.
- ⁴ Body weight will be measured while fasting, using consistent scales, after voiding, and without shoes and outerwear (eg, coats).
- ⁵ Single 12-lead ECG will be collected prior to any blood sample collection.
- ⁶ Vital signs will include DBP, SBP, and HR and will be collected prior to any blood sample collection. Patient will rest for 5 minutes prior to assessments
- ⁷ Serology for HBsAg, HCV
- ⁸ Serum pregnancy test completed in premenopausal women only. FSH test is completed in women <55 years old and >1 year without menses. Urine pregnancy test in women of childbearing potential just prior to randomization.
- ⁹ Clinical safety labs include hematology, blood chemistry, and urinalysis at all visits. Coagulation is included at Screening (Visit S1) for all patients, Baseline (Visit T1) and 3-5 days after Visit T1 only if on anticoagulants). Please refer to laboratory manual for detailed schedule of tests. A local laboratory may be used for assessment at 3-5 days after Visit T1.
- ¹⁰ Basic fasting (minimum of 10 hours) lipids include total cholesterol, calculated LDL-C, HDL-C, non-HDL-C, and triglycerides.
- ¹¹ Diet and exercise counseling per local and/or regional guidelines for the management of hyperlipidemia.
- ¹² IWRS contact at either an early withdrawal or an EOS visit to register study discontinuation visit date.
- ¹³ Depending upon the length of time between visits, 1 or 2 bottles of study medication will be dispensed as instructed by IWRS.
- ¹⁴ If patient is discontinuing treatment and completing the EOS visit, but will be continuing in the study either by returning to clinic or by phone, continue to schedule study visits for the patient according to the protocol Schedule of Events

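### Exclusion 5 lets through a first blood pressure of 185/95 but stops screening on the same reading at repeat; the definition should say 'or', not 'and'

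*Protocol*

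**What the plan says.** Criterion 5 appears in the same form in the synopsis and in Section 7.2. It has four working parts, and two other places in the protocol refer to it.

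- **Definition.** The systolic limit (160 mmHg or more) and the diastolic limit (100 mmHg or more) are joined by 'and': "160 mmHg and diastolic blood pressure (DBP".
- **Trigger for a repeat.** The note opens with "If the initial blood pressure (BP) values meet or exceed the specified level", after which one more assessment may be done.
- **Stop rule on repeat.** The connector becomes 'or': "If the systolic or the diastolic values continue to meet or exceed the threshold, the patient may not continue screening".
- **Way back in.** At the investigator's discretion, screening between S1 and S2 can run up to 4 weeks longer while blood-pressure drugs are adjusted. The dose must have been stable for at least 2 weeks before randomization, and the condition on the new reading is that "the repeat BP measurements do not meet the exclusion criteria".
- **Visit S1 procedures (Section 10.2.1).** The optional visit is for patients whose "DBP and/or SBP meet the exclusion criteria levels". They may be randomized once "the repeat BP values (DBP and/or SBP) no longer meet exclusionary values".
- **Schedule of Events, footnote 2 (Appendix 1).** Same condition: "the repeat blood pressure values (DBP and/or SBP) do not meet exclusionary values".

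Section 10.2.1 and footnote 2 set no limits of their own; they rely on criterion 5.

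**The concern.** The definition and the repeat test in one criterion use different connectors, and the two procedural texts fit the repeat test better than the definition. A patient with one raised value is therefore judged by a looser test on first reading than on repeat. The looser test comes first: on the definition alone, an isolated systolic elevation of any size does not meet criterion 5.

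This is a safety exclusion in patients with HeFH and/or ASCVD, applied at about 125 sites. Staff working from Section 10.2.1 could treat a single raised value as exclusionary, while staff working from the definition would not. That would affect which patients are randomized, how screen failures are counted by criterion (SAP Section 9) and which enrolments are recorded as deviations (SAP Section 10).

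**Working it through.** No sample-size or power figure is involved, so the check is one of logic. The inputs are the limits and connectors in criterion 5. The readings are illustrations chosen here, not values from the documents.

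Let S mean systolic ≥160 and D mean diastolic ≥100.

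- First reading: excluded if S **and** D (definition).
- Repeat, allowed once the first reading met S and D: stopped if S **or** D (note).
- After drug adjustment: re-qualifies if the exclusion criteria are not met. The natural referent is the numbered criterion, that is, not (S and D).

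**Paths under the current text**

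1. First reading 185/95: S true (185 ≥ 160), D false (95 < 100). S and D is false, so the patient is not excluded and the note is not triggered.
2. First reading 185/105: S and D both true, so a repeat is allowed. Repeat 185/95: S still true, so S or D is true and screening stops. The reading is the one that passed in path 1.
3. First reading 165/105, repeat 155/102: stopped on the diastolic value. A first reading of 155/102 would not have been excluded.
4. First reading 185/105, repeat 155/95: neither value raised, so the patient continues.
5. Path 2 followed by the extension, with 185/95 on the later assessment: S and D is false, so on the natural reading of the re-qualification test the patient can be randomized on the value that stopped them earlier.

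**All states of a reading**

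| Current reading | As first reading | As repeat after both were raised |
|---|---|---|
| Both raised | excluded, subject to repeat | stopped |
| Only systolic raised (185/95) | not excluded | stopped |
| Only diastolic raised (150/105) | not excluded | stopped |
| Neither raised | not excluded | continues |

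The outcome depends on history in 2 of the 4 states. These are logical states, not patient frequencies.

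**After each possible correction**

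- 'Or' in the definition: both single-raised states meet the criterion on first reading and on repeat. History-dependent states: 0 of 4.
- 'And' in the note: both single-raised states pass on first reading and on repeat. History-dependent states: 0 of 4.

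**The case against.** The strongest reply is that the two tests work in sequence. The definition decides who is hypertensive, and the note asks that both values come down before someone who has just met the full definition is cleared. That is a coherent safety choice. Amendment 2 also edited this note, adding the S1-to-S2 window, and left both connectors in place. Most of this stands. A reader might infer that criterion 5 contradicts itself or gives no single rule. The documents do not support that, because each path above leads to one outcome. What the reply does not explain is why the stricter test should lapse at re-qualification, where the wording returns to the definition, or why Section 10.2.1 and footnote 2 treat either value as able to be exclusionary. The Amendment 2 edit shows that the text was revisited, not which connector was meant.

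A reader might also take the stop as final. It is not: the 4-week extension can reverse it.

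Other repeat notes, such as the one for triglycerides ("For those patients who have a repeat TG, the repeat value will be used to determine eligibility"), might suggest that the defect in criterion 5 is a missing sentence of that kind. It is not. The criterion 5 note already makes the repeat decisive, and the sentence would not choose between 'and' and 'or'.

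Other protections exist. Exclusion 21 lets the investigator keep out a patient thought to be unsafe, and vital signs are taken again at S2, S3 and T1 (Sections 10.2.2 to 10.2.4). These reduce the risk but leave the threshold unaligned.

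**Conclusion.** The concern holds as a minor eligibility and safety correction. The definition in criterion 5 is looser than its own repeat test and than the sense of the two procedural texts. As a result a single raised value passes on first reading and stops screening on repeat, subject to the extension.

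The conclusion rests on a literal reading of current text and on taking the re-qualification condition to mean the numbered definition. The share of screened patients with only one raised value is not given, so no patient count can be attached. No passage shows sites applying the criterion differently; that remains a plausible risk. Nor do the documents state that 'or' was intended. It is preferred because it agrees with the note, Section 10.2.1 and footnote 2, and because it is the safer rule in this population.

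A reader might infer that trial results are at risk. They are not. Eligibility is settled before randomization, the Full Analysis Set is all randomized patients and the Safety Analysis Set is all who were randomized and dosed (SAP Sections 5.1 and 5.2). Power, alpha and the between-arm comparison are unaffected.

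**What to change.** Change 'and' to 'or' between the systolic and diastolic limits in the criterion 5 definition, in the synopsis and in Section 7.2. The trigger, the stop rule, the re-qualification test, Section 10.2.1 and footnote 2 then all follow one rule without further edits.

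If the sponsor confirms that both limits must be met, change 'or' to 'and' in the two copies of the note instead, and align Section 10.2.1 and footnote 2.

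The 'or' version costs one word in two places. It newly excludes patients with one raised value unless they clear on repeat or re-qualify after drug adjustment, so slightly more screen failures should be expected; the documents give no number. The 'and' version costs one word in two notes plus the two alignments, and keeps isolated elevations eligible. Either change needs a protocol amendment with prior IRB/IEC approval (Section 17.3) and is best bundled with another amendment.
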